identifying foods, 1b) test the validity of Nutrition AI at quantifying the amount of food provided, and 1c) assess user satisfaction and usability of Nutrition AI in Openfit among adults in Baton Rouge, Louisiana. Openfit is not currently designed to assess plate waste, though Nutrition AI has the potential to assess plate waste and ultimately food intake. Therefore, the secondary aims of this pilot study are to: 2a) test the validity of Nutrition AI to identify plate waste and, 2b) test the validity of Nutrition AI to quantify the amount plate waste, and 2c) to assess user satisfaction and usability of the Nutrition AI in Openfit to assess plate waste, among adults in Baton Rouge, Louisiana. From this data we can calculate food intake (food plated – plate waste).

Primary Hypotheses:

- 1a) Nutrition AI will correctly identify $\geq 70\%$ of foods plated with automated methods, and $\geq 80\%$ after user correction.
- 1b) Compared to weighed values, energy estimates (kcal) of foods plated, from Nutrition AI, will be:
 - i. Within error margins of 20% without user correction (automated)
 - ii. Within error margins of 15% with user correction (semi-automated)

Secondary Hypotheses:

- 2a) Nutrition AI will correctly identify $\geq 60\%$ of plate waste with automated methods, and $\geq 80\%$ after user correction.
- 2b) Compared to weighed values, energy estimates (kcal) of plate waste, from Nutrition AI, will be:
 - i. Within error margins of 20% without user correction (automated)
 - ii. Within error margins of 15% with user correction (semi-automated)

Methods

Study Design

For this pilot study, using a convenience sample, we will recruit up to 25 adults to use the Nutrition AI technology in Openfit to identify and estimate portion size of foods provided and simulated plate waste, and food intake in a laboratory setting at Pennington Biomedical Research Center (PBRC) and/or Louisiana State University (LSU). Laboratory members within the Ingestive Behavioral Laboratory will also test the ability of Nutrition AI to identify foods and to quantify foods provided, plate waste and food intake, in the laboratory. Meals will be simulated, and participants will not consume the foods provided.

Participants and Recruitment

We will recruit up to 25 adults

- Inclusion criteria include:
 - o Male or female, age 18-62 years
 - o Self-reported body mass index (BMI) 18.5-50 kg/m²

- Exclusion criteria include:

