 - o Any condition or circumstance that could impede study completion
 - o Unfamiliar with or not able to use an iPhone

NOTE: PBRC and LSU employees (vulnerable populations) will be targeted and invited to participate. The consent form will explicitly specify that if a PBRC or LSU employee chooses not to participate, there will be no impact on their employment.

Procedures

Written informed consent will initially be obtained. We will then obtain:

- Demographics (self-reported): DOB, race, ethnicity, sex, employment, income, marital status, education level (Lifestyle, Demographics, and Health Questionnaire)
- Anthropometrics (self-reported): height, weight, BMI

On being deemed eligible, participants will receive training on how to use the Openfit app housing the Nutrition AI technology. Subsequently, participants will be randomly assigned to one of five study menus (5 participants per menu) of differing calorie levels (see Table 1). Participants will use a provided smartphone to identify foods and quantify the amount of food plated (e.g., an apple) and simulated plate waste (e.g., half an apple) with Nutrition AI. Within each study menu, participants will be served two meals of a similar calorie level. These two meals will be served during the same study visit. To ensure we are testing the validity of the Nutrition AI across differing portion sizes, each meal (e.g., the chicken meal), will be tested across two different study menus where the amount of food provided and plate waste differs. The amount of plate waste will be assigned randomly using an exponential distribution, with the minimal being 0% remaining (i.e., no waste) and the maximum being 74%¹². On average we will aim for ~5% plate waste across tests to reflect average plate waste in free-living conditions¹³.

These tests will be conducted via Openfit in a laboratory-based setting at PBRC or LSU. Simulated food provision and plate waste will be covertly identified and weighed, and participants will not eat the food provided. During the study visit, tasks completed by each participant on the iPhone will be recorded using the record function on the iPhone and the recording will be saved to the iPhone camera roll. Data will be accessed from the iPhone at study completion. Consent, training, and testing will span up to ~2 hours.

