For a food identified through the Nutrition AI to be considered an exact food match, the name of the food identified must match or be a close match to the food served. For example, a fruit cocktail identified as a fruit salad is an acceptable match¹⁵. Proportions will be used to assess whether the percentage of food items plated that were correctly identified by Nutrition AI is different to the percentage of foods correctly identified by a criterion method (human rater). Descriptive data will also be used to describe the frequency at which food plated and plate waste were correctly identified.

Mean error and Bland-Altman analysis¹⁶ will be performed to determine errors in estimation of energy intake and food group servings from the Nutrition AI compared to estimations from the criterion measure¹⁷.

Responses to the user satisfaction and usability questionnaires will be assessed using frequencies and percentages for Likert scale data. Open responses will be evaluated using qualitative methods to identify common themes.

Provisions to Monitor the Data to Ensure the Safety of Subjects

Adverse events will be monitored.

Withdrawal of Subjects

Subjects may be withdrawn from the study at any time. If a subject voluntarily withdraws from the study, no additional data will be collected, and they will be considered dropouts in the study.

Risks to Subjects

This study involves no greater than minimal risk. The main risk is breach of confidentiality, and the PBRC team will work to minimize this during data collection, handling, and analysis.

Potential Benefits to Subjects

Participants may benefit by increased awareness of energy and nutrients in food served.

Sharing of Results with Subjects

Participants will have access to the study results once published.

Setting

The Ingestive Behavior, Weight Management, and Health Promotion Laboratory at PBRC, and [name] or [name] at LSU.

Compensation

Participants will receive \$50 for the successful completion of the study.

Provisions to Protect the Privacy Interests of Subjects

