All attempts will be made to maintain a subject's privacy. Safeguards such as password protected computers and networks have been put in place to limit access to subject data. Subjects will be given ample time to read over the consent, ask questions, and agree to participate in the research study. Subjects may decline to answer questions with which they are not comfortable. Each procedure will be explained to the subject before it is performed. We will always ensure the privacy of the subjects.

Compensation for Research-Related Injury

No compensation will be provided for research-related injury.

Economic Burden to Subjects

All study-related tests and procedures will be at no cost to the subject.

Consent Process

A designated and trained staff member will obtain informed consent during the visit. Ample opportunity will be given for the subject to review the consent form and ask any questions prior to signing the form. If subjects wish, they can take the form home and return at a different visit. We are aware that consent is an ongoing process.

Table 1. PortionSize AI Groups

Menu 1- 400 kcal each meal	
Burger Tomato Onion Burger bun Cheese slice Ketchup Cookies Coke	Chicken Ready Rice Oranges Carrots Butter Sweet Tea
Menu 2- 800 kcal each meal	
Chicken Ready Rice Oranges Carrots Butter Sweet Tea	Pizza Lettuce Tomato Dressing Cookies Coke
Menu 3- 500 kcal each meal	
Pizza Lettuce Tomato Dressing Cookies Coke	Pork Chop Broccoli Butter Apple Slices Sweet Tea
Menu 4- 700 kcal each meal	
Pork Chop Broccoli Butter Apple Slices Sweet Tea	Lettuce Carrot Tomato Pre-cooked frozen chicken Dressing Milk
Menu 5- 600 kcal each meal	
Lettuce Carrot Tomato Pre-cooked frozen chicken Dressing Milk	Burger Tomato Onion Burger bun Cheese slice Ketchup Cookies Coke

References

4. Willett WC. *Nutritional epidemiology*. New York: Oxford University Press; 1998.

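### The Bland-Altman analysis names no size axis; on the method's usual mean-of-two-methods axis, app error alone can create or hide a trend with portion size, so differences should be set against weighed energy.

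*Combined protocol and SAP*

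**What the plan says.** Statistical analyses gives one sentence to agreement on quantity: "Mean error and Bland-Altman analysis", for energy intake and servings of food groups, with the comparison described as "compared to estimations from the criterion measure". It names no horizontal axis, no regression of the difference on size, no test for proportional bias and no significance level.

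The criterion is weighed. Primary hypothesis 1b opens "Compared to weighed values, energy estimates (kcal) of foods plated, from Nutrition AI, will be" and then sets margins of 20% (automated) and 15% (after user correction). Procedures adds: "Simulated food provision and plate waste will be covertly identified and weighed, and participants will not eat the food provided". The outcome list calls the criterion values known.

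Portion size is varied on purpose. Procedures says "participants will be randomly assigned to one of five study menus (5 participants per menu) of differing calorie levels", and explains why each meal appears in two menus: "To ensure we are testing the validity of the Nutrition AI across differing portion sizes". Table 1 gives the nominal energy, from "Menu 1- 400 kcal each meal" through 500, 600 and 700 to 800 kcal. Each participant is served two meals of similar energy.

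**The concern.** A Bland-Altman plot in its usual form sets the difference between two methods against their average. That suits two methods with comparable error. Here one value is weighed and the other is an image-based estimate. The app's error enters the difference in full and the average by half, so the two axes are correlated even when the app is unbiased at every portion size.

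An analyst who follows the usual form and then asks how error changes with portion size could go wrong in two ways:

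- A noisy but unbiased app could appear to underestimate small meals and overestimate large ones.
- An app that really overestimates small meals and underestimates large ones could appear to have no trend.

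No other analysis in the plan addresses the portion-size question that the menus were built to answer.

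**Working it through.** **Inputs from the documents.** There are five menus with 5 participants each and two meals per participant, at nominal energy 400, 500, 600, 700 and 800 kcal per meal.

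**The plan's own count.** The burger meal is in Menus 1 and 5, so 5 × 2 = 10, which agrees with the item-level n=10 under Outcome measures. In total, 5 × 5 = 25 participants and 25 × 2 = 50 meals.

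**Assumed, not in the documents.** The per-meal error SD of the app, a two-sided 5% level, and (at first) independent normal errors. The 20% and 15% margins are hypotheses about error and are not SDs.

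**Spread of true energy.** The mean is 600 kcal. The variance of the levels is (40,000 + 10,000 + 0 + 10,000 + 40,000)/5 = 20,000, so s_W = 141 kcal.

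**Unbiased app.** Let W be weighed energy, A = W + e the app estimate, with e of mean zero, SD s and independent of W. Put D = A − W and M = (A + W)/2.

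- Slope of D on M = (s²/2) / (s_W² + s²/4)
- Correlation r = (s/2) / √(s_W² + s²/4)
- Chance of a significant slope ≈ 1 − Φ(1.96 − atanh(r)·√(n − 3)), with n = 50

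For example, at s = 120 kcal the slope is 7,200/23,600 = 0.31 and r = 60/153.6 = 0.39.

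| Error SD, % of 600 kcal | s (kcal) | Slope on M | r | False trend, 50 meals |
|---|---|---|---|---|
| 5% | 30 | 0.02 | 0.11 | 11% |
| 10% | 60 | 0.09 | 0.21 | 30% |
| 15% | 90 | 0.18 | 0.30 | 57% |
| 20% | 120 | 0.31 | 0.39 | 81% |
| 30% | 180 | 0.58 | 0.54 | 98% |

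The chance passes 50% at an SD of about 82 kcal (13.7%). Simulation with 4,000 trials per setting agrees with the table. Regressing D on W instead gives an expected slope of zero and a false-trend rate of 4.7% to 5.9% at every SD tried.

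**Sensitivity of the mean-axis result.**

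- Intake with about 5% random waste: 55% at a 15% SD and 80% at 20%.
- Meals scattered by 10% around the nominal levels: 49% and 74%.
- The two meals averaged to 25 participant values (within-person error correlation 0 to 0.5): 17% to 23% at a 15% SD, 27% to 38% at 20%, 52% to 67% at 30%.

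**Masking.** Suppose the app flattens portions, so D has true slope b on W. The covariance of D and M is half of (var A − var W), which is zero when (1 + b)² = 1 − s²/s_W².

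- At s = 90: 1 − 8,100/20,000 = 0.595, so b = −0.23. The mean axis flags a trend in about 3% of trials, the weighed axis in about 70%.
- At s = 120: 1 − 14,400/20,000 = 0.28, so b = −0.47. The rates are about 2% and 97%.

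**Shared error.** Table 1 has five meal types, each at two energy levels, so ten meal-level combinations, each imaged by five participants. I simulated this layout with 25% or 50% of the error variance shared (assumed) and ordinary regression of D on W. False-trend rates were about 7% to 9% when error was shared by meal type, and 17% to 28% when it was shared by meal-level combination. The mean axis was worse in each setting, but changing the axis does not by itself give a 5% test.

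**The case against.** The strongest reply is that the plan does not contain this error. It states no axis, no slope and no test. Outcomes 1b, 2b and 2d are errors against known values, and the hypotheses are margins of 20% and 15%. Mean error and constant limits of agreement are identical on either axis. The sentence about portion sizes explains why the menus differ and does not commit to a trend analysis. All of this stands. The mean axis is inferred from the method's usual form, and harm follows only if someone then reads a trend from the plot.

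A reader might infer that an unbiased app would usually appear to have proportional bias. The documents do not support that. They give no error SD, the rate is 30% at a 10% SD, and on participant averages it is below one half even at 20%.

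A reader might also blame the five fixed energy levels. The cause is unequal error between the two methods. The levels matter because they limit the spread of true energy, and they are nominal: meals are described as similar in energy, and the quantity named in the analysis sentence is intake after random waste.

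The reply does not remove the need for a clause. The plan sets out to examine validity across portion sizes, names one method for agreement, and leaves open a choice whose usual form is unsuited to a weighed criterion.

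**Conclusion.** The point holds as a gap with a poor default, worth closing because closing it is cheap. The direction of the artefact is algebra: it needs only a criterion with far less error than the app. Its size rests on the assumed SD and on the unit of analysis, neither of which the plan states. A false trend ranges from about 11% (SD 5%) to 81% (SD 20%) with meals taken singly, and is 27% to 38% at SD 20% on participant averages. Masking of a real flattening trend is an equal risk.

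It would be wrong to conclude that the primary results are compromised, since the mean errors and constant limits are untouched. It would also be wrong to say that the plan has chosen the mean axis. The calculations cover plated energy and energy intake. The same algebra applies to plate waste, but its size there was not calculated.

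**What to change.** Add to Statistical analyses that differences (AI minus weighed) are plotted against the weighed value, and that any trend with portion size is estimated against that value, for plated food, plate waste and food intake, in both automated and corrected modes.

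State that the slope comes from a model, or uses standard errors, allowing for two meals per participant and for error shared within meal type and meal-level combination. With only five meal types and ten combinations those shared components will be poorly estimated, so present the slope as an estimate with an interval and not as a pass-or-fail test.

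The change needs no new data and leaves mean error as planned. It costs slightly more analysis work and gives a wider interval for the slope than treating the 50 meals as independent would.
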